**C1c. Goal.** The HEAL Diabetes study addresses a critical need to identify effective, scalable, and sustainable behavioral weight-loss approaches to help medically underserved patients in the U.S. achieve substantial weight loss and diabetes remission. We will compare primary biological outcomes (body weight, number of prescribed blood pressure medications, A1c, and diabetes remission), secondary metabolic outcomes (fasting glucose, insulin, insulin resistance, lipid profile, and CRP levels), and secondary patient-reported outcomes (self-efficacy, self-care activities related to general diet and exercise, health-related quality of life, and average pain rating) at baseline and 12-months. Based on DiRECT and MODEL study experience and evidence from other key studies and systematic reviews, we hypothesize that the HEAL Diabetes intervention will result in weight loss  $\geq 10$  kg and diabetes remission in over 40%, self-efficacy in plant-forward healthy eating will mediate its effects on primary biological outcomes, and it will be operationally and financially sustainable.

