**Other Factors.** Covariates will be measured at baseline. These will include demographic characteristics, marital status, education level, insurance, chronic conditions, and SDOH (using electronic health record data collected on all Health Hub clients), and health literacy. At baseline, 6-, and 12-month visits, we will assess prescribed medications. Exposure to each component intervention will be assessed using health coach attendance logs.

**C11. Analysis.** We will evaluate the extent to which the program was implemented according to the protocol, examine if all components of the intervention were delivered in a standardized and reproducible format, and summarize the trial as a flow diagram following Consolidated Standards of Reporting Trials (CONSORT) guidelines. Patient characteristics will be compared between study groups to assess integrity of the random assignment process. Data will be presented as means and standard deviations for continuous variables and as frequencies and percentages for categorical variables. Results will be analyzed based on intention-to-treat.

For Aim 2, we will use baseline, 6-, and 12-month follow-up data to compare differences between treatment and control group means in continuous primary biological outcomes (body weight, blood pressure, and A1c) and secondary patient-reported outcomes (self-care activities related to general diet and exercise). We will use the MIXED procedure of SAS because this is a parallel groups trial with repeated measures assessed over time. In the context of repeated measures ANOVA, we will use t-tests within group to detect change from baseline to 12-months (Follow-up 3) and t-tests between groups to detect the effect of the treatment on the various outcome variables at 12-months. While the preceding hypothesis tests are *a priori* and not adjusted, other comparisons at the intermediary assessments will be adjusted using the Bonferroni method. To examine a difference in the proportion of patients who achieved diabetes remission at 12-month, we will use a chi-square test.

For Aim 1, we will assess intervention operational sustainability as detailed above and in **Table 3**. Based on MODEL study experience providing MI-based HC and TM interventions, we hypothesize that operational sustainability will be high with 12-month program retention rates of approximately 85-90%.

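### The 12-month tests of several co-equal primary outcomes carry no stated multiplicity adjustment, no lead outcome is named, and within-arm change tests rank equally with the randomised contrast

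*Combined protocol and SAP*

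**What the plan says.** Section C11 (Analysis), Aim 2, sets out the tests. For the continuous outcomes, "we will use t-tests within group to detect change from baseline to 12-months (Follow-up 3) and t-tests between groups" are planned at 12 months within a repeated-measures model. The next sentence gives both kinds of test a priori status and leaves them uncorrected, while "other comparisons at the intermediary assessments will be adjusted using the Bonferroni method". Remission comes after that sentence: "To examine a difference in the proportion of patients who achieved diabetes remission at 12-month, we will use a chi-square test". Nothing is said about adjusting it.

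Several outcomes are primary, and the list is not stable:
- C1b, Aim 2: body weight, blood pressure with the number of prescribed blood pressure medications in brackets after it, A1c and remission.
- C1c: "primary biological outcomes (body weight, number of prescribed blood pressure medications, A1c, and diabetes remission".
- Table 3: body weight; systolic and diastolic pressure together with a medication count; A1c and remission.
- C11: "continuous primary biological outcomes (body weight, blood pressure, and A1c", with remission handled separately.

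The document states no significance level, sidedness, testing order or rule for declaring effectiveness. C4e describes the sample of 72 as pragmatic, and C1, C4e and D present the study as a pilot giving preliminary evidence.

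**The concern.** Two features of C11 need attention.

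First, the correction falls on the supporting time points and not on the time point that decides the question. Specifying a test in advance does not control error across several primary outcomes. With no lead outcome, a nominally significant result on any one of them could be offered as the evidence of effectiveness.

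Second, within-arm tests of change from baseline have the same standing as the randomised comparison. They do not estimate a treatment effect. C4b requires A1c of at least 6.5% at screening, and C8 says baseline measures are taken at that same visit, so some fall in A1c may occur without treatment. The exclusion of A1c of 12% or more may also affect how far A1c drifts; the documents do not allow the net shift to be quantified. Controls receive an education session and produce vouchers (Table 1), so change is plausible in both arms. The hypothesis in C1c (weight loss of at least 10 kg, remission in over 40%) is written without a control comparator, so a change in the treatment arm alone could seem to meet it.

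**Working it through.** **The plan's own figure.** C4e gives no power or alpha. Its one attrition calculation is 72 × (1 − 0.15) = 61.2, stated as about 61. This reproduces.

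**Inputs for the false-positive rate**
- Between-arm tests at 12 months: four if blood pressure counts once (weight, blood pressure, A1c, remission); five if systolic and diastolic are separate; six if the medication count is tested as well.
- Level per test: two-sided 0.05. This is an assumption, since the documents give none.
- Null case: no effect on any outcome.

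**Independent tests.** The chance of at least one false positive is 1 − 0.95^m.
- m = 4: 1 − 0.95^4 = 18.5%
- m = 5: 1 − 0.95^5 = 22.6%
- m = 6: 1 − 0.95^6 = 26.5%

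**Correlated tests.** Independence is not realistic. Remission is defined partly by A1c, and C2a reports that remission is strongly associated with weight loss. Simulating equally correlated normal test statistics (200,000 draws) gives:

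| Tests | correlation 0.3 | 0.5 | 0.7 |
|---|---|---|---|
| 4 | 17.4% | 15.5% | 13.0% |
| 5 | 20.7% | 18.2% | 14.9% |
| 6 | 24.2% | 20.8% | 16.3% |

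**Check at the expected sample size.** A second simulation (20,000 replicates) used 31 and 30 completers, t-tests on weight, one blood pressure measure and A1c, and a chi-square on remission derived from A1c. It assumed an overall remission rate of 13.6%, the sum of the 12.1% partial and 1.5% complete remission in C2a. At least one between-arm false positive occurred in 18.0%, 17.6% and 16.2% of replicates at correlations 0, 0.3 and 0.5 between the continuous outcomes.

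For four to five tests the range is therefore 13.0% (four tests, correlation 0.7) to 22.6% (five independent tests).

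**Within-arm tests.** Three continuous primaries in two arms give at least 3 × 2 = 6 further unadjusted tests. They are left out of the range because their null hypothesis, no change over time, says nothing about the treatment effect.

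**Cost of Holm over four outcomes.** The first step needs p < 0.05/4 = 0.0125. With 31 and 30 completers there are 59 degrees of freedom, and a two-sample t-test has 80% power at 0.05 for a standardised difference of about 0.73. The critical value rises from 2.00 to 2.58, and power for that difference falls to about 61%. This is the strictest step; later steps are easier.

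**The case against.** The strongest reply is that this is a pilot. Its sample size is pragmatic, it is meant to estimate an effect size and supply data for larger studies, and it states openly that the 12-month t-tests are not adjusted. Whether to adjust in such a trial is partly a matter of judgement, and a compulsory correction would cost power that a sample of 72 can ill afford. This stands as a reason not to insist on Holm. It does not remove the need for a rule, because C11 still presents these as hypothesis tests of primary outcomes, including "t-tests between groups to detect the effect of the treatment on the various outcome variables at 12-months".

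A reader might also infer more than the documents support:
- **That about 1 in 5 is the error rate for all the 12-month tests, within and between arms.** It describes only four to five between-arm tests near independence, at an assumed alpha. Correlation lowers it, and within-arm tests do not belong in it.
- **That the plan declares remission unadjusted.** The statement about not adjusting precedes the chi-square sentence; on remission the plan is silent.
- **That a within-arm change will be reported as success.** This is conjecture. The between-arm tests are prespecified in the same sentence. What the text shows is equal status, which leaves the possibility open.
- **That correcting for multiplicity is nearly free.** The fall from 80% to about 61% power says otherwise.

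**Conclusion.** The concern holds in a limited form. C11 leaves the 12-month t-tests of the continuous primary outcomes unadjusted, corrects only the intermediate comparisons, states no adjustment for remission, and gives within-arm change tests the same standing as the randomised contrast. No section names a lead outcome or a rule for claiming effectiveness, and the four descriptions of the blood pressure outcome leave the number of tests open.

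The between-arm risk of at least one false positive is roughly 13% to 23% for four to five tests. That rests on an assumed two-sided 0.05 per test, no effect on any outcome, and correlations from 0 to 0.7; counting the medication count as a sixth test would raise it. Pilot status lowers the seriousness. This should be corrected in the analysis plan before outcomes are analysed, but it does not undermine the design.

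**What to change.** 1. Make the between-arm contrast at 12 months the only test of effectiveness. Report within-arm changes as means with confidence intervals and no p-values.
2. Name one 12-month between-arm outcome as primary and state its alpha and sidedness. Treat the others, including remission if it is not chosen, as secondary, reported as estimates with confidence intervals in keeping with pilot status.
3. Give the blood pressure outcome a single definition across C1b, C1c, Table 3 and C11.

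This changes wording only and needs no new data, visits or participants. The named outcome loses no power. The drawback is that the outcomes not named lose confirmatory status.

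If the investigators prefer to keep several primary outcomes, Holm across a fixed list that includes remission is an option. The list must be settled first, and the power loss at the first step shown above should be acknowledged in the plan.

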## **C12. Study Limitations (Potential Problems and Alternative Approaches)**

1. Poor intervention fidelity. Every effort will be made to ensure key intervention fidelity in all arms. For example, if a health coach resigns, their patient panel will be distributed among the other health coaches within or across health systems as has been done the MODEL study to avoid any interruptions in care.

2. Low participant recruitment or retention. It is possible that we will experience difficulties recruiting interested patients or that more than 20% of the participants will fail to complete the study, but we think this is unlikely given our MODEL study experience. In MODEL, we have recruited 672 similar T2D patients from the same clinics with 90% retention overall thus far. To prevent difficulties, we will closely monitor participants, discuss recruitment and retention at regular meetings, identify reasons for problems, and implement changes accordingly. If all retention strategies fail, we will increase number of participants to maintain adequate power.

## **D. Study Timeline and Future Directions**

We expect that this study will provide preliminary evidence regarding the effectiveness of the *HEAL Diabetes* multicomponent intervention in improving weight and blood pressure and achieving diabetes remission. These results will provide pilot data for larger studies demonstrating the effectiveness of nutrition-based multi-component interventions as an alternative to pharmaceutical treatment alone for obese patients with early T2D. Our future research will focus on assessing: 1) long-term success in weight maintenance and diabetes remission, 2) comparative cost-effectiveness of bariatric surgery vs. a multicomponent behavioral intervention, 3) relative effectiveness of component interventions in supporting behavior change and sustained weight loss, 4) refinements of the multicomponent intervention model to strengthen most powerful intervention components, 5) impact of payment policy changes for multicomponent obesity interventions on Medicaid and other vulnerable populations, and 6) effectiveness of multicomponent interventions for additional high-risk populations including the broader population with obesity, those with prediabetes, and those with multiple chronic conditions associated with obesity.

## **E. Data Collection.**

Collection Method. Data will be collected from a combination of EHR records accessed through REDCap or EPIC sourced from UTHSC Health Hub activities, blood samples, blood pressure readings, and weigh-ins, as well as from surveys and questionnaires conducted at baseline, 6-, and 12-months.

Viewing and Collecting. We will collect: a) Name, contact information, primary care contact information, medications, demographic data, comorbidity information, income, b) HbA1c levels, blood pressure readings, and weight data, c) scores on standardized tools (diabetes management and self-efficacy).

Deidentifying Data. Key personnel will deidentify data and participants will have unique participant ID numbers stored in REDCap. Access to the files will require permission from the program director, a UTHSC password, and IRB personnel approval. For each user, REDCap will require a REDCap profile, username, and password to enter the program. Study personnel will only have access to the database if the data manager has given them access. Any PHI fields will be stored in a separate form from other data collection forms. Data will be completely de-identified once the last assessment phase is complete. At this time the link between ID number and study data will be destroyed. Study data in the form of hard copies will be stored in a locked file cabinet managed by the program director and will be destroyed 3 years after completion of the study.

**F. Data and Safety Monitoring Plan.** Monitoring of the study is important for both assessment of safety of the intervention and interpretation of study results. We have a system for monitoring, scheduling, and tracking participants. Staff roles will clearly be delineated and there will be ongoing monitoring of the health education, nutrition support, and the health coaching provided. Participants will be followed for approximately one year. For any serious adverse event reported during the study, the nature, date of onset, duration, and resolution will be recorded. A co-investigator will monitor each participant for serious adverse events. If the serious adverse event is thought to be related to study participation by either the primary care provider and/or the physician investigators ([name]), the investigator may request the participant to undergo a physical examination, psychiatric evaluation, and/or laboratory testing whenever appropriate local to the participant. All staff members are trained on the FDA and IRB criteria and policies for a Serious Adverse Event. Study staff will be trained in assessing and reporting serious adverse events for all study populations.

## **F1. Medical Monitoring.**

**F1a. Investigator and study team only.** Monitoring of the study is important for both assessment of safety of the intervention and interpretation of study results. We have a system for monitoring, scheduling, and tracking participants. Staff roles will clearly be delineated and there will be ongoing monitoring of the health education

and the HC provided. Participants will be followed for approximately one year. For any serious adverse event reported during the study, the nature, and date of onset and resolution (duration), intensity will be recorded. A co-investigator will monitor each participant for serious adverse events. If the serious adverse event is thought to be related to study participation by either the primary care provider and the physician investigators ([name]), the investigator may request the participant to undergo a physical examination, psychiatric evaluation, and/or laboratory testing whenever appropriate local to the participant. All staff members are trained on the FDA and IRB criteria and policies for a Serious Adverse Event. Study staff will be trained in assessing and reporting potential serious adverse events for all study populations.

**F1b. Monitoring the Progress of Trials and the Safety of Participants.** This study will be overseen by the Principal Investigator (PI) who is an MD, a Co-Investigator MD, a study statistician, program manager, and the research coordinator. The study will be monitored by the study team on an on-going basis for protocol compliance and adequate study progress. Every month after recruitment commences, the team will review the following information in detail: Subject accrual rate; Subject drop-out and the reasons for drop-out; Gender recruitment rate; Major and minor problems related to interventions; Subject compliance with the protocol; and Program Manager and/or Research Coordinator questions or concerns. Researchers are directly involved with this review so decisions about changes, modifications, or adaptations are decided and acted upon immediately.

It is anticipated that medical problems will occur during the study. The following is a summary of the plan of action based on the level of acuity of the problem. We do not expect major issues, emergencies, or urgent problems related to our intervention; however, in the case of these events, we will address these issues as outlined in the following paragraph. Emergent problems or those problems that are life threatening or require life-saving attention should be dealt with using the Emergency Medical System (EMS) by calling 911. For any events occurring at the intervention site (UTHSC Health Hub), health hub staff will provide basic life support as an interim measure when appropriate until EMS personnel arrive. The health hub staff will be responsible for notifying the participant's family or designated contacts and the participant's primary care physician. For events occurring outside of the health hub setting, participants will be instructed to call 911, and go to the nearest emergency room. Urgent medical problems or those problems that require the immediate attention but that do not require life-saving attention should be dealt with by taking measures to ensure the participants comfort and offering first aid as appropriate under the direction of the primary care physician at the respective site. Disposition plans should be made with the involvement of the participant, health hub staff, investigators, primary care physician and the participant's family or designated contacts should always be notified.

General medical problems or those problems that require attention should be dealt with by the primary care physician. The health hub staff should follow the primary care provider's directions regarding treatment, disposition, and follow-up. Documentation of the problem and actions taken should be placed in the participant's record. See Adverse Events for additional information.

**F1c. Serious Intercurrent Illness Unrelated to the Study.** If the participant has a major illness, is hospitalized, or has other physical issues that interfere with the assigned study intervention, participation in the study will be suspended until routine health is resumed by the participant. The study physician will determine whether or not it is medically safe to continue the study. If the participant has a major illness (i.e., broken bone, etc.) that does not interfere with the assigned study intervention, the study physician will determine whether it is safe for the participant to continue participation in the study.

**F2. Data Safety and Monitoring.** This study will be conducted in accordance with all applicable federal requirements for subject privacy and safety.

**F2a. Informed Consent.** Written consent will be obtained from each participant by study staff at the screening visit (SV) and reviewed with the participant prior to each of the subsequent visits for data collection purposes (i.e., surveys, blood draws). It will become part of the permanent study record. Each participant will be assured that study participation is voluntary and that they may withdraw at any time for any reason without jeopardizing their future care at this institution. At the time of obtaining written consent, the study staff/investigators will advise participants of the experimental nature of the study, the duration of the trial, alternate modes of treatment, and prevalent adverse events that might occur. Each participant will be questioned to ascertain whether they have understood the information. An opportunity for questions and discussion will be provided for each participant. The participant's signature on the consent form is required prior to the collection of any study measures and, if applicable, randomization. Each participant will receive a copy of the informed consent statement. The informed consent statement will be reviewed and approved by the Institutional Review Board (IRB) of the University of Tennessee prior to recruitment of participants.

**F2b. Education on the Protection of Human Subjects.** All key individuals responsible for the design and conduct of this research project have received education on the protection of human research participants. The curricula consisted of Internet computer-based training for researchers at the University of Tennessee. Study staff that will be hired for this project at a future date will also receive appropriate education on the protection of human research participants prior to interacting with the study participants.

**F2c. Education on HIPAA.** All key individuals responsible for the design and conduct of this research project have received education on protection and confidentiality of protected health information (PHI). We do not envision the risks to participants to be above that of a diabetic receiving health education from their primary physician or health educator. However, implementation of this intervention may increase a participant's risk for developing hypoglycemic episodes or hyperglycemic episodes. Although this study is associated with minimal risk, an independent, institutional data and safety monitoring will be appointed before enrollment of participants into the study.

**F2d. An independent Data and Safety Monitoring Board (DSMB).** DSMB will be formed prior to the enrollment of the participants. We plan to have this committee review the final protocol for the study and to periodically review study data for the occurrence of outcomes of interest. We will specifically ask the committee to address serious adverse events and the risk to benefit profile for all study participants. The DSMB will meet a minimum of once each year and be composed of five persons, who are not involved in the study in another capacity, with expertise in any one of the following fields: medicine, endocrinology, clinical trials, epidemiology, psychology, and biostatistics. Guidelines for recommendations for changes in the study protocol will be refined for use by the DSMB. The committee will review these guidelines and make recommendations for changing any component of the trial based on regular review of all pertinent study data.

- [name], who is a co-investigator on this project, will have responsibility for analyzing interim data and preparing data and safety monitoring reports that the committee will review. These reports will include data on all adverse events and study outcomes for all study participants. [name] will be an ex-officio member of the committee and will not be blinded to participant group assignment. After the start of participant enrollment, we plan to conduct data and safety monitoring meetings in-person or via conference call twice a year. Data and safety monitoring reports will be sent to all committee members prior to the conference call.
- A Manual of Procedures will be developed for the study and the procedures will be strictly followed. All controlled trials personnel are trained in sessions that will cover all study procedures, including recruitment, informed consent, measurements, randomization, participant follow-up, and adverse events. Adherence to the procedures in the operations manual will be assured by periodic assessment and retraining. A co-investigator will monitor each participant for adverse events throughout the study using participant report and reports by primary care physician. All participants will be asked at each study visit about emergency visits, hospital visits, or other serious adverse events in the intervening period, and these reported events will be recorded in the study database. If significant differences in adverse events noted above are found, additional interviews of the participant experiencing these adverse events may be conducted at the discretion of the DSMB and any necessary remedial action taken will be recorded. At any point a participant may be withdrawn from the study for health-related reasons. Medical side effects of improvements in healthy eating, physical activity, and medication adherence will be explained as part of the informed consent process to each participant by trained study personnel and participants will be provided a copy of the informed consent statement that will include a written list of potential side effects prior to randomization. An attempt will be made to quantify the severity of each side effect by asking the participant to grade its importance or impact on quality of life.
- All participants will be encouraged to contact the study site if any episodes of severe hypoglycemia, hyperglycemia, or hospitalizations of any nature occur. In addition, physicians will be asked to notify the study site of any hospitalizations or severe episodes of hypoglycemia or hyperglycemia. Conversely, if the UTHSC Health Hub personnel uncover a morbid event in a study participant, the study staff will contact the participant's personal health care provider. The participants will have access to study personnel or to one of the physician investigators by telephone 24 hours each day through the on-call system in the event of medical problems related to the study. Our health systems have on-call systems that give the participants access to a physician investigator 24 hours a day. To further ensure participant safety, during the follow-up period we plan to assess wellbeing by physical assessment including blood pressure.

**F3a. Adverse Events.** We define serious adverse events as any adverse event or adverse reaction that results in death, is life-threatening, requires hospitalization or prolongation of existing hospitalization, results in persistent or significant disability or incapacity, or congenital anomaly or birth defect. We define adverse events as any untoward medical occurrence in a participant or experimental investigation subject administered a study treatment and which does not necessarily have a causal relationship with this treatment. Because this is a pragmatic trial with minimal risks we will only be recording and reporting serious adverse events such as severe hypoglycemia, or less serious, hyperglycemia.

**F3b. Classification of Events.** In this study, the likelihood of serious adverse events associated with the planned interventions is very low, and mostly consists of a small possibility of serious hypoglycemic or hyperglycemic reactions associated with improvements in health habits as detailed below. All adverse events will be classified as to whether they are serious or not serious. An adverse event is considered serious if it is life threatening, prolonged or permanently disabling, requires or prolongs hospitalization for any cause other than routine delivery, is a congenital anomaly, or a major cardiovascular event. An event may also be considered serious if an investigator judges it to be a significant hazard or contraindication to continued study intervention or use of study medication. In addition, we will classify all adverse events regarding the relationship, severity, and expectedness as described below.

**Relationship** The following are expected adverse events that may occur during the trial:

**Related to Intervention.** Potential adverse events (AE) known to be associated with caloric restriction, weight loss, or improved medication adherence in patients with diabetes: hypoglycemia, hyperglycemia, malnutrition, bone loss, gall bladder disease. The DiRECT trial which employed a similar intervention found that severe hypoglycemia occurred between 0.2 to 0.57 times per 100 patient years in the treatment arm over the first 4 years of the study. Potential AE's known to be associated with exercise in patients with diabetes: hypoglycemia, fracture or other injury, cardiac arrhythmia, cardiovascular event.

**Related to condition under study.** Potential AE's known to be associated with overweight or obesity include: diabetes, hypertension, dyslipidemia, cardiovascular disease (CVD), gall bladder disease, liver disease. All patients will be monitored at every data collection visit through the 12-month visit for the occurrence of these adverse events.

**Severity** During the trial participants will be queried to determine if a serious adverse event has occurred as described above and all adverse events will be identified through patient and provider report. All serious adverse events will be recorded. A serious adverse event is considered serious if it is life threatening, prolonged or permanently disabling, requires or prolongs hospitalization for any cause other than routine delivery, is a congenital anomaly, a major cardiovascular event, or cancer other than non-melanoma skin cancer. An event may also be considered serious if an investigator judges it to be a significant hazard or contraindication to continued study intervention or use of study medication.

**Expectedness** Adverse events will also be classified as to whether they are expected or unexpected. An unexpected adverse event is one for which the nature or severity is not consistent with information about the condition under study or intervention in the protocol, consent form, or program brochure. An expected event is one known to be associated with the intervention or condition under study. Thus, expectedness is related both to the intervention and to the condition under study. All serious or unexpected adverse events related to the intervention will be reported to the IRB and to the sponsor in a timely manner.

**F3c. Data Collection Procedures for Adverse Events.** As described above, a co-investigator will monitor each participant for serious adverse events throughout the study using participant and provider reports. All patients will be asked at each study visit about emergency visits, hospital visits, or other serious adverse events in the intervening period, and these reported events will be recorded in the study database and concordance with the registry assessed as described above. Participants will be asked at each study visit about any serious adverse events that may have occurred between study visits. All participants will be encouraged to contact the study site if untoward symptoms, illnesses, or hospitalizations of any nature occur. In addition, their relatives and their personal physicians will be asked to notify the study site of any hospitalizations or major illnesses. Conversely, if the health hub personnel uncover a morbid event in a study participant, the study staff will contact the participant's personal health care provider.

